### **Statement of Compliance to protocol, GCP and applicable regulatory guidelines:**

This trial will be conducted in compliance with the protocol, ISO 14155, the International Conference on Harmonization Good Clinical Practice E6 (ICH-GCP), the Declaration of Helsinki, and all applicable regulatory requirements.

**CHANGE HISTORY**

Version	Originator	Description of Change(s) and Section Number(s) Affected	Date
1.0	[REDACTED]	Original Protocol	22 January 2019
2.0	[REDACTED]	Updated base curve value of the Acuvue OASYS lens, updated slit lamp procedures concerning timing of lid eversion, corrected error in exclusion #13 Added package insert for Dailies AquaComfort Plus	27 February 2019
3.0	[REDACTED]	Corrected lens fit assessment parameters	06 March 2019
4.0	[REDACTED]	Removed need to collect worn lenses for analysis Specified subjective grading of lid margin staining from photos Ancillary supplies table updated	16 April 2019

**Clinical Study Protocol**  
**Johnson & Johnson Vision Care, Inc.**

5.0	████████	To enable recruitment of the targeted number of symptomatic subjects, the total number of subjects which can be enrolled was increased. Study responsible clinician at JJVC changed to █████. Clarified numbering of visits in Part 2.	30 October 2019
6.0	████████	Updated pregnancy language in section 13.5 Updated to v10 of protocol template Updated biostatistician and reviewer Added COVID language to Protocol Compliance Signature Page Added Appendix O – █████	23 September 2020

**Clinical Study Protocol**  
**Johnson & Johnson Vision Care, Inc.**

**SYNOPSIS**

Protocol Title	Late night study 2: End-of-Day Assessment of Asymptomatic and Symptomatic Soft Lens Wearers
Sponsor	JJVC, [name], [name]
Clinical Phase	Development phase, Phase 0
Trial Registration	This study will be registered on ClinicalTrials.gov by the Sponsor
Test Article(s)	Investigational Products: Dailies AquaComfort Plus daily disposable contact lenses Acuvue Oasys 1-Day daily disposable contact lenses
Wear and Replacement Schedules	Wear Schedule: daily wear Replacement Schedule: daily disposable

# Clinical Study Protocol

## Johnson & Johnson Vision Care, Inc.

Objectives	
Primary Objectives: Part 1: to investigate if there are statistically significant differences in the following clinical measures between asymptomatic and symptomatic contact lens wearers:
 

1. Upper and lower lid margin lissamine green staining (14 hours)

2. Non-invasive tear break-up time (NIBUT) (14 hours)

3. Tear meniscus height (TMH) (14 hours)

4. Tear film osmolarity (14 hours)

5. Density of white blood cells in the eyelid margins using confocal microscopy (6 hours)

 
These will be referred to as the 'five clinical measures'
 
Secondary Objectives: Part 1 and 2: To investigate any possible relationship between subjective scores of contact lens comfort and the five clinical measures.
 
Other Objectives:
 

1. Part 2: to investigate differences in the five clinical measures between asymptomatic and symptomatic contact lens wearers.

2. Part 1 and 2: To investigate if end-of day comfort following lens removal returns to pre-lens wear comfort levels.

3. Part 1 and 2: To provide frozen samples of tear film for further laboratory analysis which will be outlined in separate laboratory protocols.

4. To investigate the relationship between difference in CLDEQ-8 score between Part 1 and 2 and the difference in the five clinical measures between Part 1 and 2.

5. To investigate the relationship between difference in CLDEQ-8 score between Part 1 and 2 and the difference in the (follow-up minus baseline) and (follow-up minus fitting) values between Part 1 and Part 2 for all clinical measures except density of white blood cells.

6. Part 1 and 2: To investigate the change from baseline and fitting in all the clinical measures except density of white blood cells in the eyelid margins for asymptomatic and symptomatic subjects.

------------	---

# Clinical Study Protocol

## Johnson & Johnson Vision Care, Inc.

Study Endpoints	
Primary endpoints: Lid margin staining grade, NIBUT, TMH, tear film osmolarity, mean density of white blood cells
 
Secondary endpoints: VAS comfort scores
 
Other endpoints: Change from baseline, change from fitting, CLDEQ-8 and change in CLDEQ-8

Study Design	
This is a 2-Part, 8-Visit, single-center, open-label, bilateral and dispensing clinical study. In Part 1 (Visits 1-4) all subjects will be dispensed Dailies AquaComfort Plus, in Part 2 (Visits 5-8) all subjects will be dispensed Acuvue Oasys 1-Day.
 
Part 1            Approximately 210-240 subjects will be recruited and fitted with Dailies AquaComfort Plus over approximately a two-week period in order to identify ~27 asymptomatic (CLDEQ-8 score less or equal to 10) and ~27 symptomatic (CLDEQ-8 score more than or equal to 20). Only those subjects classified as asymptomatic or symptomatic at the end of Visit 2 (~54 subjects) will be asked to continue. Visits 3 and 4 will take place in the early morning and after <math>14 \pm 2</math> hours respectively, on a single study day.
 
Part 2            Subjects who complete Part 1 (~ 54 subjects) will continue onto Part 2. The visit procedures will be the same as for Part 1 but subjects will use the Acuvue Oasys 1-Day lens.
 
See the flow chart at the end of the synopsis table for the schematic of the study visits and procedures of main observations (Figure 1)

Sample Size	Part 1, Visits 1 & 2: ~210-240 subjects Part 1, Visits 3 & 4: ~54 subjects Part 2: ~54 subjects
Study Duration	The study will last approximately 18 months and will include a 9-month recruitment period.
Anticipated Study Population	Habitual soft contact lens wearers aged 18-45 years will be stratified into asymptomatic and symptomatic lens wearers based on their CLDEQ-8 score.

# Clinical Study Protocol

## Johnson & Johnson Vision Care, Inc.

Eligibility Criteria	
Potential subjects must satisfy all of the criteria listed in Section 3.2 to be enrolled in the study.
 
Inclusion Criteria after Screening
 

1. They are 18-45 years of age (inclusive).

2. They understand their rights as a research subject and are willing and able to sign a Statement of Informed Consent.

3. They are willing and able to follow the protocol.

4. They agree not to participate in other clinical research while enrolled on this study.

5. They currently use daily disposable soft daily wear contact lenses (worn bilaterally) (within the last six months) which may be spherical, toric or multifocal.

6. They agree to wear their lenses for at least 12-14 hours per day.

7. They own a wearable pair of spectacles (by self report).

 
Inclusion Criteria after Baseline
 

8. They have a spherical contact lens prescription in the range +6.00 to -10.00 DS (based on the calculated ocular refraction).

9. They have up to a maximum of 1.00 DC of refractive astigmatism (based on the calculated ocular refraction).

10. They have best corrected distance visual acuity of at least 0.20 binocularly.

 
Potential subjects who meet any of the following criteria will be excluded from participating in the study:
 
Exclusion Criteria after Screening:
 

1. They have an ocular disorder which would normally contraindicate contact lens wear.

2. They have a systemic disorder which would normally contraindicate contact lens wear.

3. No ocular topical medications (including comfort drops) from 24 hours prior to study visits or during the wear of any study lenses.

4. They are regularly using anti-inflammatory or pain medications (i.e. medication routinely used more than twice per week).

5. They have had cataract surgery.

6. They have had corneal refractive surgery.

7. They are pregnant or breast-feeding.

8. They have any infectious disease (e.g. hepatitis) or any immunosuppressive disease (e.g. HIV) or a history of anaphylaxis or severe allergic reactions.

----------------------	---

[figure not shown]
**Clinical Study Protocol**  
**Johnson & Johnson Vision Care, Inc.**

	
9. They are an employee or immediate family member of an employee of the clinical site (e.g. Investigator, Coordinator, Technician).
 
10. They have taken part in any other clinical trial or research within two weeks prior to starting this study.
 
11. History of allergy to sodium fluorescein or lissamine green.
 
Exclusion Criteria after Baseline:
 
12. They have any corneal distortion e.g. as a result of previous rigid lens wear or have keratoconus.
 
13. They have any slit lamp findings of Efron Grade 3 or greater (e.g. corneal oedema, corneal neovascularization, tarsal abnormalities, conjunctival injection) or findings of < Grade 3 which in the investigator's opinion would contraindicate contact lens wear.

Disallowed Medications/Interventions	
No ocular topical medications (including comfort drops) from 24 hours prior to study visits or during the wear of any study lenses.
 
No systemic medications that in the view of the investigator may affect the ocular surface or contact lens wear from 24 hours prior to study visits.
 
No regular use of anti-inflammatory or pain medications (i.e. medication routinely used more than twice per week).

Measurements and Procedures	Lid margin staining, NIBUT, TMH, tear film osmolarity, VAS comfort score, logMAR VA, lens fitting measurements, white blood cells using confocal microscopy.
Microbiology or Other Laboratory Testing	Tear film cytokine investigations
Study Termination	The occurrence of one or more Unanticipated Adverse Device Effect (UADE), or any SAE where relationship to study agent cannot be ruled out, will result in stopping further dispensing of investigational product.
Ancillary Supplies/ Study-Specific Materials	Any Sponsor-approved saline pods
Principal Investigator(s) and Study Institution(s)/Site(s)	A full list of Principal Investigators, clinical sites, and institutions is kept separately from the Study Protocol and is included in the study Trial Master File.

# Clinical Study Protocol

## Johnson & Johnson Vision Care, Inc.

Figure 1: Study Flowchart (Note: In Part 2, the visits are Visit 5 to Visit 8)

# Clinical Study Protocol

## Johnson & Johnson Vision Care, Inc.

### COMMONLY USED ABBREVIATIONS AND DEFINITIONS OF TERMS

ADD	Plus Power Required For Near Use
ADE	Adverse Device Effect
AE	Adverse Event/Adverse Experience
BCVA	Best Corrected Visual Acuity
BSCVA	Best Spectacle Corrected Visual Acuity
CFR	Code of Federal Regulations
CLUE	Contact Lens User Experience
COAS	Complete Ophthalmic Analysis System
COM	Clinical Operations Manager
CRA	Clinical Research Associate
CRF	Case Report Form
CRO	Contract Research Organization
CT	Center Thickness
<hr/>	
D	Diopter
DMC	Data Monitoring Committee
eCRF	Electronic Case Report Form
EDC	Electronic Data Capture
ETDRS	Early Treatment Diabetic Retinopathy Study
FDA	Food and Drug Administration
GCP	Good Clinical Practice
HIPAA	Health Insurance Portability and Accountability Act
IB	Investigator's Brochure
ICF	Informed Consent Form
ICH	International Conference on Harmonization
IDE	Investigational Device Exemption
IEC	Independent Ethics Committee
IRB	Institutional Review Board
ISO	International Organization for Standardization
ITT	Intent-to-Treat
JJVC	Johnson & Johnson Vision Care, Inc.
LC	Limbus Center
LogMAR	Logarithm of Minimal Angle of Resolution
MedDRA ®	Medical Dictionary for Regulatory Activities
MOP	Manual of Procedures
NIBUT	Non-invasive tear break up time
NIH	National Institutes of Health
OD	Right Eye
OHRP	Office for Human Research Protections
OHSR	Office for Human Subjects Research
OS	Left Eye
OU	Both Eyes
PD	Protocol Deviation
PHI	Protected Health Information

# **Clinical Study Protocol**

## **Johnson & Johnson Vision Care, Inc.**

PI	Principal Investigator
PIG	Patient Instruction Guide
PQC	Product Quality Complaint
PRO	Patient Reported Outcome
QA	Quality Assurance
QC	Quality Control
SAE	Serious Adverse Event/Serious Adverse Experience
SAP	Statistical Analysis Plan
SAS	Statistical Analysis System
SD	Standard Deviation
SOP	Standard Operating Procedure
TMH	Tear meniscus height
UADE	Unanticipated Adverse Device Effect
USADE	Unanticipated Serious Adverse Device Effect
VA	Visual Acuity

# **Clinical Study Protocol**

## **Johnson & Johnson Vision Care, Inc.**

### **1. INTRODUCTION AND BACKGROUND**

The study design and the objectives were based on the results obtained through previous clinical work (████████ and █████████) which showed that clinical parameters such as lid margin staining, tear film osmolarity, NIBUT, tear meniscus height (TMH) and the appearance of white blood cells in the lid margin are different in asymptomatic and symptomatic soft lens wearers. This study aims to confirm the results obtained and attempts to replicate the previous findings with Dailies AquaComfort Plus (DACP) and then to explore the potential impact on the findings using the same methodology with Acuvue Oasys 1-Day (O1D). Utilizing this approach will allow us to identify the best endpoints to predict end-of-day contact lens discomfort.

#### **1.1. Name and Descriptions of Investigational Products**

The products used in this clinical study are:

Dailies AquaComfort Plus (Alcon) daily disposable contact lenses  
Acuvue Oasys 1-Day (JJVC) daily disposable contact lenses

Both lenses are CE marked. Further details about the test articles are found in Section 6 of this protocol.

#### **1.2. Intended Use of Investigational Products**

The lenses will be used as indicated i.e. for daily wear, daily disposable use. Each lens type will be worn bilaterally for a two-week period and then followed up with an additional single study day. Subjects will be encouraged to wear the lenses for 12-14 hours during the two-week wear period and then for  $14 \pm 2$  hours on the ensuing study single visit day.

Only subjects who are classified as asymptomatic or symptomatic will go on to wear the second lens type (O1D). Asymptomatic subjects are defined as those with a CLDEQ-8 score less or equal to 10 and symptomatic subjects are defined as those with a CLDEQ-8 score of more than or equal to 20.

#### **1.3. Summary of Findings from Nonclinical Studies**

Not Applicable – marketed products only.

#### **1.4. Summary of Known Risks and Benefits to Human Subjects**

This study will use approved marketed products. The following risks/adverse events can be associated with the use of any marketed contact lens:

- Discomfort, pain, watering or unusual secretions of the eyes
- Redness of the eyes
- Reduced vision and sensitivity to light
- In very rare instances corneal infection, scarring or permanent loss of vision may occur

The key invasive procedures in this work and their associated risks are outlined below:

# **Clinical Study Protocol**

## **Johnson & Johnson Vision Care, Inc.**

### Confocal microscopy

- Some temporary discomfort on manipulation of the eyelids
- Some temporary discomfort during the procedure itself

### Staining of the ocular surface with sodium fluorescein

- Some temporary discomfort on application
- Very rarely, anaphylaxis with topical application

### Staining of the lid margins with lissamine green

- Some temporary discomfort on application
- No known cases of anaphylaxis with topical application

There is no direct benefit to the subjects enrolled other than being able to try a lens or lenses that they have not had the opportunity to try before. The information obtained from this study may aid in the development of improved contact lenses in the future.

In order to minimise the likelihood of adverse events, subjects will undergo an ocular examination before and after the clinical investigations. Subjects will also be trained on what to do if they develop ocular discomfort, redness or reduced vision and what to do if they need to be seen outside of the Eurolens Research clinic opening hours.

For the most comprehensive risk and benefit information regarding DACP and O1D refer to the latest version of the package insert of the marketed products (Appendix C).

### **1.5. Relevant Literature References and Prior Clinical Data Relevant to Proposed Clinical Study**

All lenses being investigated in this work are CE marked/approved and marketed products. (APPENDIX C: PACKAGE INSERT (APPROVED PRODUCT)).

Two previously completed JJVC clinical study reports:

[name]. [REDACTED] *Clinical study report version 1.0: End-of-Day clinical assessment of asymptomatic and symptomatic soft contact lens wearers.* April 6, 2018.

[name]. [REDACTED] *Clinical study report version 1.0: Confocal microscopy of the eyelid margin as a surrogate for contact lens discomfort.* June 12, 2018.

## **2. STUDY OBJECTIVES, ENDPOINTS AND HYPOTHESES**

### **2.1. Objectives**

Primary Objectives

# **Clinical Study Protocol**

## **Johnson & Johnson Vision Care, Inc.**

To investigate if there are statistically significant differences in the following clinical measures between asymptomatic and symptomatic lens wearers:

1. Upper and lower lid margin lissamine staining (14 hours)
2. NIBUT (14 hours)
3. TMH (14 hours)
4. Tear film osmolarity (14 hours)
5. Density of white blood cells in the eyelid margins using confocal microscopy (6 hours)

These will be referred to as the five clinical measures.

Secondary Objective(s)

Part 1 and 2: to investigate any possible relationship between subjective scores of contact lens comfort and the five clinical measures.

Other Objectives

1. Part 2: to investigate differences in the five clinical measures between asymptomatic and symptomatic contact lens wearers
2. Part 1 and 2: to investigate if end-of day comfort following lens removal returns to pre-lens wear comfort levels.
3. Part 1 and 2: to provide frozen samples of tear film for further laboratory analysis which will be outlined in separate laboratory protocols.
4. To investigate the relationship between difference in CLDEQ-8 score between Part 1 and 2 and the difference in the five clinical measures between Part 1 and 2.
5. To investigate the relationship between difference in CLDEQ-8 score between Part 1 and 2 and the difference in the (followup – baseline) and (followup – fitting) values between Part 1 and Part 2 for all the clinical measures except density of white blood cells.
6. Part 1 and 2: to investigate the change from baseline and fitting in all the clinical measures except density of white blood cells in the eyelid margins for asymptomatic and symptomatic subjects.

### **2.2. Endpoints**

Primary Endpoint(s)

The primary endpoints in this study are lid margin lissamine green staining grade, NIBUT, TMH, tear film osmolarity at the beginning and the end of a lens-wearing day (after 14 hours). Additionally, the number of white blood cells in the lid margins after 6 hours of lens wear will be investigated.

#### Lid margin staining

# **Clinical Study Protocol**

## **Johnson & Johnson Vision Care, Inc.**

Lid margin staining of the upper and lower eyelids will be performed in the left eye (OS) only using lissamine green. The staining will be graded both subjectively at the time of the clinic visit and also objectively using automated image analysis software from photographs. Images should be collected as soon as possible for best image quality, and grading can be conducted using a slit lamp or from the images.

For the subjective grading the following will be graded for each eyelid:

Horizontal length of staining

Sagittal width of staining

Average staining grade – this is the average of the horizontal and sagittal grades for each eyelid

A final grade will be calculated which is the average of each eyelid's average staining grade.

For the objective image analysis three metrics of staining will be evaluated; (1) Staining Area, (2) Staining Intensity and (3) Staining thickness

### Non-invasive Break-up Time (seconds)

NIBUT will be measured using the Medmont topographer for the right eye (OD) only. Three measurements will be undertaken.

### Tear Meniscus Height (mm)

The lower tear meniscus in the right eye (OD) only will be imaged using optical coherence tomography (OCT). Three images will be taken.

### Tear Film Osmolarity

Tear film osmolarity will be collected in the right eye (OD) only using the Tearlab (Tearlab Corp.) Two measurements will be collected.

### White Blood Cells (mean density of cells)

Images, using Confocal Microscopy will be taken in both eyes for both the upper and lower eyelid in the central lid area. These images will be used to determine the density of inflammatory white blood cells.

### Secondary Endpoints

Contact lens comfort will be assessed at the beginning and at the end of day ( $14 \pm 2$  hours post lens insertion) using a visual analogue scale (VAS) ranging from 0 – 100, where 0 is uncomfortable and 100 is comfortable.

### Other Endpoints

Change from baseline and 14 hours and change from fitting and 14 hours (where appropriate) for the following clinical measures:

- upper and lower lid margin staining
- NIBUT
- TMH
- tear film osmolarity

# **Clinical Study Protocol**

## **Johnson & Johnson Vision Care, Inc.**

CLDEQ-8 score and change in CLDEQ-8 score

### **2.3. Hypotheses**

Primary Hypotheses

For Part 1:

1. Symptomatic subjects will have, on average, statistically significantly, greater upper and lower lid margin staining compared to asymptomatic subjects after 14 hours of lens wear.
2. Symptomatic subjects will have, on average, statistically significantly, shorter NIBUT compared to asymptomatic subjects after 14 hours of lens wear.
3. Symptomatic subjects will have, on average, statistically significantly, lower TMH compared to asymptomatic subjects after 14 hours of lens wear.
4. Symptomatic subjects will have, on average, statistically significantly, greater tear film osmolarity compared to asymptomatic subjects after 14 hours of lens wear.
5. Symptomatic subjects will have, on average, statistically significantly, greater density of white blood cells (visualized by confocal microscopy) in both the upper and lower lid margins compared to asymptomatic subjects after 6 hours of lens wear.

Secondary Hypotheses:

For Part 1 and 2

1. There is a statistically significant relationship with at least one of the five clinical measures (lid margin staining, NIBUT, TMH, tear film osmolarity and density of white blood cells) and subjective comfort measured using VAS grading scales at 14 hours (6 hours for white cells).

Other Hypotheses:

For Part 2:

1. Symptomatic subjects will have, on average, statistically significantly, greater upper and lower lid margin staining compared to asymptomatic subjects after 14 hours of lens wear.
2. Symptomatic subjects will have, on average, statistically significantly, shorter NIBUT compared to asymptomatic subjects after 14 hours of lens wear.
3. Symptomatic subjects will have, on average, statistically significantly, lower TMH compared to asymptomatic subjects after 14 hours of lens wear.
4. Symptomatic subjects will have, on average, statistically significantly, greater tear film osmolarity compared to asymptomatic subjects after 14 hours of lens wear.

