### 14.4. Level of Statistical Significance

Each pre-planned primary and secondary hypothesis will be analyzed with a two-sided type I error rate of 5%.

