# Clinical Study Protocol

## Johnson & Johnson Vision Care, Inc.

- Unstructured Covariance Structure (UN)
- Homogenous Compound symmetry (CS)

The structure that returns the lowest Akaike Information Criteria Corrected (AICC) will be selected as the structure that best fit the data. Heterogeneous covariance structures across strata may be considered if necessary. The Kenward and Roger method (Kenward and Roger, 1997) will be used for the denominator degree of freedom.

The Comparison between the symptomatic and the asymptomatic strata will be carried out using one-sided 95% confidence intervals for the Least-squares means risk ratio (symptomatic over asymptomatic) at 6-hour follow up for the hypothesis given below:

$$\begin{aligned} H_0: \mu_S / \mu_A &\leq 1 \\ H_A: \mu_S / \mu_A &> 1, \end{aligned}$$

where S=Symptomatic and A=Asymptomatic. Adjustments for multiple comparisons across lower and upper lid margins will be performed using a simulation method with alpha equal to 0.05 (Edwards and Berry, 1987). A statistically significantly greater density of WBC, on average, in both the upper and lower lid margins for symptomatic subjects compared to asymptomatic subjects after 6 hours of lens wear will be concluded if the multiple adjusted lower limit of the 95% confidence intervals for the Least-squares means risk ratio is above 1.0.

**Remark:** For all the above models, the Kenward and Roger method implemented with the *kr2* option in SAS will be used for the calculation of the denominator degrees of freedom. Heterogenous models across subject strata may be considered. The log-likelihood ratio test will be used to test for homogeneity between the two strata. Convergence limitations will be taken into account as necessary. If convergence is problematic, then reduced versions of the corresponding model will be considered. When the normality assumption does not hold for an endpoint, the analysis will be conducted on transformed data; generalized linear models or generalized linear mixed models with appropriate distributions will also be considered on the original data.

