### 14.6. Secondary Analysis (For Part 1 and Part 2)

#### Relationship between Comfort Scores and Clinical Measures

Correlation analysis will be conducted between subjective comfort scores (VAS scale) and primary endpoints. Pearson product-moment correlation coefficient will be provided for continuous endpoints and Kendall's tau coefficient will be provided for ordinal endpoints. For each of the primary endpoints, when there is more than one measurement taken for each subject (eye for WBC), the mean will be used in the analysis and a test based on the corresponding correlation coefficient will be conducted separately.

Tests for the relationship between the comfort scores and each of the primary endpoints will be conducted separately using two-sided 95% confidence intervals constructed for the corresponding correlation coefficient. The relationship between comfort scores and a primary

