# Clinical Study Protocol

## Johnson & Johnson Vision Care, Inc.

endpoint will be concluded to be significant if 0 does not fall within confidence limits of the corresponding coefficient. The directional statistical relationship will be determined using the upper or lower limit of the 95% confidence interval. Upper limit below zero or lower limit above zero of the 95% confidence will determine negative or positive relationship, respectively, between the clinical measure and the VAS score. Further analysis based on a linear model or a generalized linear model depending on the distribution of the VAS scale may be undertaken if necessary when the relationship between comfort scores and any one of primary endpoints is significant.

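### The single secondary hypothesis is met if any one of five measures relates to comfort, yet its assigned 5% error rests on five unadjusted 95% intervals: about 18–23% per Part if no measure is related

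*Combined protocol and SAP*

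**What the plan says.** Protocol section 2.3 lists one secondary hypothesis, under a line that covers Parts 1 and 2: "There is a statistically significant relationship with at least one of the five clinical measures", namely "lid margin staining, NIBUT, TMH, tear film osmolarity and density of white blood cells", and VAS comfort. One related measure out of five is enough to meet it.

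Section 14.4 sets the error rate: "Each pre-planned primary and secondary hypothesis will be analyzed with a two-sided type I error rate of 5" per cent.

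Section 14.6 gives the analysis. Tests of comfort against "each of the primary endpoints will be conducted separately using two-sided 95% confidence intervals", and the relationship with a primary "endpoint will be concluded to be significant if 0 does not fall within confidence limits of the corresponding coefficient". The section concludes measure by measure. It gives no adjustment, ordering or gatekeeping across the five measures, no rule for declaring the at-least-one hypothesis met, and no statement of how the two Parts combine.

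The multiplicity adjustments the plan does state are in section 14.5 and run across the two lids only, in the first lid margin staining model and in the white blood cell model: "Adjustments for multiple comparisons across lower and upper lid margins will be performed using a simulation method with alpha equal to 0.05".

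Section 14.1 says a stand-alone SAP will give more detail before database lock. It is not among the documents supplied.

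**The concern.** Section 2.3 words the secondary hypothesis as a union: any one of five findings meets it. Section 14.4 attaches 5% to that hypothesis. Five separate looks at 5% each cannot deliver 5% for the union unless the tests are practically identical.

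Section 1 says the study is meant to identify the best endpoints for predicting end-of-day discomfort, and section 4.2 foresees a later meta-analysis. A report that the secondary hypothesis was met at the 5% level would be read as stronger evidence than the planned tests supply.

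**Working it through.** **Inputs.** Five measures (section 2.3). Two-sided 5% per secondary hypothesis (section 14.4). One unadjusted 95% interval per correlation (section 14.6). Planned sample 27 per stratum, 54 in total (section 14.2). The documents give no correlations among the measures or between Parts, so ranges are assumed below.

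**The plan's own figure.** One correlation in one Part: 1 − 0.95 = 5%. This reproduces.

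**The hypothesis as worded, one Part, independent measures.** 1 − 0.95^5 = 22.6%. This does not reproduce 5%.

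**Correlated measures.** With equal correlation ρ among the five test statistics and c = 1.96, the rate is

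1 − ∫ φ(x) [Φ((c − √ρ·x)/√(1−ρ)) − Φ((−c − √ρ·x)/√(1−ρ))]^5 dx.

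This was checked by simulation: 54 subjects, normal data, Fisher-z 95% intervals, no true relationship, 20,000 runs per setting.

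| Inter-measure correlation (assumed) | 0 | 0.3 | 0.5 | 0.7 | 0.9 |
|---|---|---|---|---|---|
| Five unadjusted intervals, formula | 22.6% | 20.9% | 18.3% | 14.8% | 10.2% |
| Five unadjusted intervals, simulation | 22.6% | 21.3% | 18.3% | 15.4% | 10.9% |
| Holm across the five, simulation | 5.1% | 4.9% | 4.2% | 3.7% | 2.6% |

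A second simulation (6,000 runs) used Kendall's tau for an ordinal staining grade, overdispersed counts for white cells and skewed VAS scores. It gave 22.5%, 19.3% and 13.2% at correlations 0, 0.5 and 0.9, so the result does not depend on normal data.

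**How the Parts combine.** The documents state no rule, so both possibilities are shown for inter-measure correlation 0 to 0.5 and between-Part correlation 0 to 0.8.
- Either Part suffices: 1 − 0.95^10 = 40.1% if all ten tests are independent; 30–40% over the range.
- Both Parts required: 0.226^2 = 5.1% if independent; about 3–9% over the range.

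**Adjusted threshold.** Holm's smallest adjusted p-value is five times the smallest raw p, so it reaches 0.05 when the raw p is 0.01. Error for independent tests: 1 − 0.99^5 = 4.9%. Pearson |r| needed with n = 54 on the Fisher scale: tanh(1.96/√51) = 0.268 at 5% and tanh(2.576/√51) = 0.346 at 1%.

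**The case against.** The strongest reply is that section 14.6 never makes the union claim. It tests and concludes each measure separately at a valid 5%, and the only follow-on is an optional further model. The objective in section 2.1 is looser still. Adjusting across endpoint-specific secondary correlations in an early development study is partly a matter of preference. This stands as far as the individual correlations go: a reader might infer that the five tests are invalid, and they are not. It does not rescue section 2.3, which does make the claim, or section 14.4, which attaches 5% to it.

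A reader might also take 40% as the error rate of the plan. That needs a rule that either Part suffices, and no passage states one. The line covering Parts 1 and 2 can equally be read as applying to each Part, and if both were required the rate would be close to nominal.

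Third, subjects are selected from the extremes of the CLDEQ-8, and section 1 reports earlier differences between such groups, so it is unlikely that no measure at all relates to comfort. True: the rates here are not the expected chance of a false claim. But a type I error rate is defined under that null, and 5% is what the plan assigns.

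Finally, the stand-alone SAP may contain an adjustment. That cannot be excluded; the supplied text has none for this analysis.

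**Conclusion.** The point holds, confined to the at-least-one claim. Within one Part, if no measure relates to comfort, the hypothesis would be declared met about 18–23% of the time for inter-measure correlations of 0 to 0.5. That is 3.7 to 4.5 times the assigned 5% (18.3/5 and 22.6/5). A rate near 10% needs a correlation of about 0.9 among all five, which is hard to expect of measures as unlike as staining, osmolarity and cell counts. Across Parts the rate cannot be fixed, because the combination rule is missing. The correlations are assumptions; the 22.6% under independence is exact.

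The primary analysis is not affected. This is a mismatch among three statements that should be aligned before database lock.

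**What to change.** Choose one.

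(a) Reword the secondary hypothesis in section 2.3 as five relationships, reported separately for each Part, each at 5%, with no at-least-one claim. This matches how section 14.6 already concludes, and costs no power.

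(b) Keep the claim but make it separately for each Part. Declare it met only if the smallest Holm-adjusted p-value across the five correlations is no greater than 0.05, that is, the smallest raw p is no greater than 0.01. Keep the unadjusted 95% intervals as descriptive and amend the significance sentence in section 14.6. The two Part-level claims must not then be merged into one that either Part can satisfy, since 1 − 0.99^10 = 9.6%. The cost is power: with 54 subjects a Pearson |r| of about 0.35 is needed rather than 0.27. The threshold differs for Kendall's tau, and for white cells in Part 2 if fewer subjects are imaged, since step 6.11 limits confocal imaging to those classified as asymptomatic or symptomatic.

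Both are text edits only.

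A separate, minor clarification concerns white cells. Section 14.6 says that "when there is more than one measurement taken for each subject (eye for WBC), the mean will be used in the analysis", which leaves the unit of analysis open. State one value per subject, averaged over both eyes. Also reconcile the six-hour comfort score that section 2.3 names for white cells with the VAS items collected at Visits 2 and 6 (steps 2.7 and 6.7), which are two recalled scores for the two-week wearing period.
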